5.4 Dosage Adjustments

5.4.1 Withholding of Study Drug

Subjects with symptomatic orthostatic hypotension and/or systolic BP < 85 mmHg, which in the medical judgment of the Investigator would interfere with subject's ability to safely receive study drug, will have study drug withheld until the next scheduled monthly administration, but should still have all other study visit assessments completed.

5.4.2 Management of Suspected Systemic Infusion-Related/Hypersensitivity Adverse Events

In the event of a suspected systemic infusion-related and/or hypersensitivity AE, the infusion should be immediately discontinued and appropriate supportive therapy should be administered per institutional practice, which may include, but is not limited to, epinephrine, IV fluids, corticosteroids, vasopressors, oxygen, bronchodilators, antihistamines, or acetaminophen/paracetamol. Subjects should be evaluated and carefully monitored until there is complete resolution of the AE (i.e., all hypersensitivity signs and symptoms have resolved). In addition to the institution's recommended assessments, blood samples should be obtained in the event of a suspected systemic infusion-related and/or hypersensitivity AE for assessment of the following: cytokine levels (IL-6, IL-8, TNF-alpha, and INF-gamma) complements C3, C4, and CH50; C-reactive protein (CRP), serum amyloid A/acute phase serum amyloid A (SAA/A-SAA); tryptase (serial levels: within 30 to 120 minutes of onset AND at 48 to 72 hours); serum NEOD001; and anti-NEOD001 antibody levels.

For subjects with a Grade 2 infusion-related AE, if it is appropriate to restart the infusion, the infusion rate should be decreased by 50% (e.g., if the infusion was previously administered over 60 minutes, the new rate should be based on administering 250 mL over at least 90 minutes). If the subject is to receive additional infusions in subsequent weeks, the rate of these infusions should be discussed with and agreed upon prospectively by the Investigator and the Medical Monitor. In addition, for all subsequent infusions, maximal premedication must be administered according to institutional practice and should include an H1 blocker, an H2 blocker, an antipyretic such as acetaminophen/paracetamol and a steroid (e.g., 25-50 mg hydrocortisone IV).

If a subject experiences a Grade 3 infusion-related and/or hypersensitivity AE, the infusion should not be restarted. The decision to continue dosing this subject at their next scheduled administration should be discussed with the Medical Monitor. If the decision is made to proceed with subsequent dosing, **both** the dose and infusion rate will be reduced by 50% from the original dose (i.e., 12.5 mg/kg in 250 mL) and infusion rate (i.e., over at least 90 minutes [if the previous infusion time was 60 minutes]). In addition, maximal premedication must be administered according to institutional practice and should include an H1 blocker, an H2 blocker, an antipyretic such as acetaminophen/paracetamol and a steroid (e.g., 25-50 mg hydrocortisone IV). Subjects who have an infusion-related and/or hypersensitivity AE at the subsequent scheduled study drug administration must have study drug permanently discontinued and have an ETD Visit per [Section 6.2](#).

Subjects who experience a Grade 4 infusion-related and/or hypersensitivity AE must have study drug permanently discontinued and have an ETD Visit per [Section 6.2](#).

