5.3 Dosage, Preparation, and Administration

Study drug consists of NEOD001 or placebo. The NEOD001 dose is 24 mg/kg; however, the maximum dose administered is not to exceed 2500 mg. Therefore, subjects with a weight of 104.2 kg or greater will receive the maximum dose of 2500 mg. The subject's weight during Screening may be used for calculation of the first dose. Subsequent doses may be calculated based on the current weight at that visit or using the Screening weight, based on the site's institutional guidelines. A change of $\pm 10\%$ from the weight being used for dosing should trigger recalculation of the dose based on the new weight unless thought to be exclusively due to fluid fluctuation (e.g., edema).

Each vial of 500 mg of NEOD001 will be reconstituted with 9.6 mL sterile WFI to a concentration of 50 mg/mL resulting in a buffered, isotonic, preservative-free solution with a total extractable volume of 10 mL. Study drug will be prepared in a 250 mL IV bag of 0.9% saline. The equivalent volume of reconstituted NEOD001 will be withdrawn prior to transferring the drug solution into the IV bag, such that the total IV bag volume will be 250 mL. A separate placebo will not be provided for this study. Subjects who receive placebo will be administered a 250 mL IV bag of 0.9% saline, which will look identical to the NEOD001 infusion bag. Refer to the Pharmacy Manual for complete information on preparing and administering the study drug.

The Unblinded Pharmacy Staff at each site will be responsible for preparing the study drug; all other study team members, including the Sponsor and site monitor must remain blinded to study drug assignment. The Unblinded Pharmacy Staff will obtain the treatment assignment information from the IWRS, and will then prepare and reconstitute the study drug, providing it to the Investigator for administration. The Unblinded Pharmacy Staff will maintain the records for drug accountability for audits or inspections. An Unblinded Monitor will be assigned as the Sponsor's designee to perform drug accountability and as such, will be the Unblinded Pharmacy Staff's primary point of contact for any study drug-related issues.

The study drug should only be administered in settings where emergency resuscitative equipment and personnel trained in the management of anaphylaxis are immediately available to treat systemic reactions under the direct supervision of a physician.

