2.2.4. Study Drug

Study drug consists of NEOD001 or placebo. The NEOD001 dose is 24 mg/kg (not to exceed 2500 mg). Each vial of 500 mg of NEOD001 will be reconstituted with 9.6 mL sterile water for injection to a concentration of 50 mg/mL, resulting in a buffered, isotonic, preservative-free solution with a total extractable volume of 10 mL. Study drug will be prepared in a 250 mL IV bag of 0.9% saline. The equivalent volume of reconstituted NEOD001 will be withdrawn from the IV bag prior to transferring the drug solution into the IV bag, such that the total IV bag volume will be 250 mL. A separate placebo will not be provided for this study. Subjects who are assigned to the placebo group will be administered a 250 mL IV bag of 0.9% saline, which will look identical to the NEOD001 infusion bag. The volume contained in the administration tubing

should be completely flushed using approximately 30 mL of 0.9% Sodium Chloride Injection after administration of study drug.

Please refer to the protocol for complete product details.

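### Protocol 5.4.2 gives half of the 24 mg/kg dose as 12.5 mg/kg with no cap (correct: 12 mg/kg, at most 1250 mg), and its 90-minute floor guarantees only a 33% lower infusion rate

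*Protocol*

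**What the plan says.** The full dose appears in both documents. Protocol 5.3: "The NEOD001 dose is 24 mg/kg; however, the maximum dose administered is not to exceed 2500 mg". SAP 2.2.4: "The NEOD001 dose is 24 mg/kg (not to exceed 2500 mg". Protocol 5.3 adds that subjects of 104.2 kg or more receive the 2500 mg maximum. Study drug is prepared in a 250 mL bag, and infusions after the first may run over 60 minutes.

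Protocol 5.4.2 then sets the rules after an infusion reaction.

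- **Grade 2, restart of the infusion:** "the infusion rate should be decreased by 50% (e.g., if the infusion was previously administered over 60 minutes", in which case "the new rate should be based on administering 250 mL over at least 90 minutes". For infusions in later weeks, "the rate of these infusions should be discussed with and agreed upon prospectively by the Investigator and the Medical Monitor".
- **Grade 3, later dosing:** "The decision to continue dosing this subject at their next scheduled administration should be discussed with the Medical Monitor". If dosing continues, "the dose and infusion rate will be reduced by 50% from the original dose (i.e., 12.5 mg/kg in 250 mL", with the rate given as "over at least 90 minutes [if the previous infusion time was 60 minutes".

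Protocol 5.4.3 separately allows a 50% dose reduction for drug-related adverse events, but prints no mg/kg figure.

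**The concern.** Both paragraphs state a percentage and then a worked figure, and a site will usually act on the figure. The Grade 3 dose is introduced with 'i.e.', so 12.5 mg/kg is offered as the meaning of the rule and not as a rounded example. Nothing else in either document corrects it. It would be half of 25 mg/kg, a dose that the documents do not give for this trial.

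These instructions are for subjects with cardiac amyloidosis who have just reacted to the infusion. A site that follows the printed figures gives more drug than the rule allows, and may give it faster. Two sites could read the same paragraph, deliver different doses or rates, and both claim compliance. A monitor would have no clear basis for calling either one a deviation.

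**Working it through.** **Inputs.** Full dose 24 mg/kg, maximum 2500 mg (protocol 5.3, SAP 2.2.4). Bag volume 250 mL and usual infusion time 60 minutes after the first infusion (protocol 5.3). Required reductions of 50%, and the printed figures of 12.5 mg/kg and at least 90 minutes (protocol 5.4.2).

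**Dose, up to the cap weight.**
- The printed figure is not reproduced: 0.5 × 24 = 12.0 mg/kg.
- Reduction actually given: 1 − 12.5/24 = 47.9%.
- Excess over the half dose: 12.5/12 − 1 = 4.2%.
- At 104.2 kg: 12.5 × 104.2 = 1302.5 mg, against 0.5 × 2500 = 1250 mg.

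**Dose, above the cap weight.** The full dose stays at 2500 mg, so half stays at 1250 mg, while a literal 12.5 mg/kg keeps rising. The eligibility criteria (protocol 4.1 and 4.2) set no upper weight limit. The weights of 110 and 125 kg are assumed for illustration.

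| Weight | Full dose | Literal 12.5 mg/kg | Reduction | Excess over 1250 mg |
|---|---|---|---|---|
| 110 kg | 2500 mg | 1375 mg | 45.0% | 10% |
| 125 kg | 2500 mg | 1562.5 mg | 37.5% | 25% |

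Correcting 12.5 to 12 is not enough for these subjects. At 110 kg, 12 mg/kg without a cap is 1320 mg, a 47.2% reduction. Of the 125 mg excess at that weight, 1375 − 1320 = 55 mg comes from the wrong figure and 1320 − 1250 = 70 mg from the missing cap.

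**Rate.** Rate = volume / time.
- Over 60 minutes: 250/60 = 4.17 mL/min.
- Half of that: 2.08 mL/min, so the time needed is 250/2.083 = 120 minutes.
- Over 90 minutes: 250/90 = 2.78 mL/min, a reduction of 1 − 60/90 = 33.3%.
- Running at the 90-minute floor is 2.778/2.083 = 1.33 times the half rate.

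**Grade 3, dose and rate together.** The original delivery is 24/60 = 0.400 mg/kg/min. As printed, at the floor, it is 12.5/90 = 0.139, which is 65% lower. With both halvings done exactly it is 12/120 = 0.100, which is 75% lower.

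**The case against.** The arithmetic of 12.5 against 12 cannot be defended. The objections concern the rate and the consequences.

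**The rate text does not contradict itself.** This stands. A reader might infer that the 90 minutes conflicts with the 50% rule. It does not: both paragraphs set a minimum, and 120 minutes satisfies the rule and the minimum together. What remains is that 90 minutes satisfies the minimum and fails the rule.

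**In the Grade 3 paragraph, rate could mean drug per minute.** On that scale the printed figures give a 65% reduction, more than the 50% required. This reading does not hold. Halving the dose in the same 250 mL over the same time already halves drug per minute, so the separate instruction to cut the rate as well would do nothing. The Grade 2 example also expresses rate as volume over time.

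**Perhaps a 50% longer infusion was meant, since 60 × 1.5 = 90.** Possible, but neither document states such a rule. Both paragraphs order a 50% lower rate. Keeping 90 minutes on this guess would turn the 50% safety rule into a 33% one.

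**The 4.2% excess is trivial, given that protocol 5.3 tolerates a 10% weight change before the dose is recalculated.** This comfort is not available above 104.2 kg, where the excess reaches 10% at 110 kg and goes on rising. It also compares unlike things: weight drift, and a deliberate reduction after a reaction.

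**Other safeguards exist.** This largely stands. After a reaction the infusion stops and the subject is monitored until complete resolution. A Grade 2 restart happens only if appropriate, and continued dosing after a Grade 3 reaction requires discussion with the Medical Monitor and maximal premedication. For the same-day Grade 2 restart, however, 5.4.2 writes in no Medical Monitor agreement on the rate. The Pharmacy Manual may carry the right figures, but it is not part of the documents.

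**Conclusion.** The Grade 3 dose figure is wrong as written. It should be 12 mg/kg with a maximum of 1250 mg. The error is a 47.9% reduction in place of 50% up to 104.2 kg, and it grows with weight because no cap is printed: 45% at 110 kg, and 37.5% at an assumed 125 kg. The figures above the cap weight assume that a site applies 12.5 mg/kg literally.

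The rate part holds only as a loose floor. On volumetric rate, and for the protocol's own 60-minute case, it allows a reduction as small as 33%.

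The point is minor. Protocol 1.3.2 reports infusion reactions with under 1% of infusions in the completed Phase 1/2 study, and likewise in the blinded Phase 3 study, where premedication is required. All were Grade 1 or 2, so few subjects should reach these paragraphs. A reader might infer that the trial's results are at risk, but the documents do not support that. The reduced dose plays no part in the efficacy analyses, power or type I error. Confidence is high on the dose figure. On the rate, the arithmetic is certain but the drafters' intent is not.

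**What to change.** 1. In the Grade 3 paragraph of protocol 5.4.2, define the reduced dose as *50% of the original dose (i.e., 12 mg/kg, maximum 1250 mg, in 250 mL)*.
2. In the Grade 2 and Grade 3 paragraphs, replace 90 minutes with 120 minutes as the minimum where the previous infusion took 60 minutes. Keep the 50% rule as stated.
3. Check that the Pharmacy Manual gives the same figures.

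The cost is a short administrative amendment of a few words in two paragraphs, and an infusion up to 30 minutes longer (120 − 90) for the few subjects affected. The SAP needs no change.

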5.4.3 Dose Reductions

Dose reductions may be allowed in the event that AEs are observed that are believed to be related to study drug, and which in consultation between the Investigator and the Medical Monitor, may be managed by a 50% reduction in dose. The duration of the dose reduction will be at the Investigator's discretion.

5.5 Treatment Compliance

Treatment compliance will be documented in the eCRF by recording the date, time, and whether or not each IV dose of study drug was completely infused, along with reasons why treatment was adjusted or not administered, if applicable.

5.6 Prior and Concomitant Medication/Therapy

Prior and concomitant medications include any drug (investigational, prescription, or over-the-counter) or biological product (such as vaccines, blood or blood components) including herbal remedies or preparations. All prior/concomitant medications taken or received by a subject within the 28 days prior to the Month 1-Day 1 Visit through the EOS/ETD Visit, and any changes to concomitant medications during the study will be recorded on the appropriate eCRF.

5.6.1 Allowed (Concomitant)

- Radiation therapy for the treatment of local amyloid deposits
- Calcium channel blockers (if on stable dose)
- Steroids (*exception*: not allowed for treatment of AL amyloidosis)

5.6.2 Prohibited (Concomitant)

- Chemotherapy
- Other investigational agents (e.g., drugs not approved for any indication)

- Myeloablative chemotherapy with ASCT
- Organ transplant
- Histone deacetylase (HDAC) inhibitors
- Doxycycline use (if required for treatment of infection, contact the Medical Monitor)
- Gadolinium contrast agents are only permitted in exceptional circumstances. If a patient requires the use of gadolinium contrast agents, contact the Medical Monitor.
- Experimental imaging of amyloid

6 STUDY PROCEDURES

6.1 Evaluations by Visit

6.1.1 Screening

With the exception of the assessments to be considered standard of care (e.g., NT-proBNP/BNP, tissue samples, and echocardiograms), a signed ICF must be obtained before any study-specific screening evaluations are performed and should be documented in the subject's medical chart.

Screening evaluations and procedures will be performed within 28 days prior to the first study drug administration on Month 1-Day 1. Individual test results that do not meet eligibility requirements may be repeated, *with the exception of* 6MWT; full rescreening is allowed once per subject.

The following will be performed within the 28 days prior to the Month 1-Day 1 Visit:

- Signed ICF
- Review inclusion and exclusion criteria to assess eligibility
- Medical History - Obtain comprehensive cardiac, hematologic, and oncologic medical history; additionally, for all other conditions obtain relevant medical history for the past 5 years (including all major hospitalizations and surgeries), as well as the subject's current medical status
- If available, record results of at least 2 prior NT-proBNP or 2 prior BNP measures from within the previous 6 months; NT-proBNP is preferred, but BNP may be used if it is the institution's historical standard
- Prior and concomitant medications/therapy
- Assessment of AEs
- Confirmation of AL amyloidosis by mass spectrometry tissue typing, immunoelectron microscopy, gene sequencing, and/or ^{99m}Tc scintigraphy for subjects who meet Inclusion Criterion #3
- Complete physical examination - including height, weight, and examination of general appearance; head, ears, eyes, nose, and throat; neck; skin; cardiovascular system; respiratory system; gastrointestinal system; and nervous system. The following should be assessed: macroglossia, submandibular nodes/fullness, adenopathy, ecchymoses, liver/spleen size (palpable +/-), ascites (+/-), and edema (which should be quantified on a scale of 0-4).
- Vital signs – heart rate (HR), BP, respiratory rate (RR), and body temperature after the subject has been at rest for ≥ 5 minutes
- ECOG PS ([Appendix 7](#))

- NYHA class ([Appendix 8](#))
- NIS-LL ([Appendix 5](#) and [Section 6.6.2.5](#)) and VASPI ([Appendix 6](#) and [Section 6.6.2.5](#))
 - Note: NIS-LL is for all subjects with peripheral neuropathy at Screening and the addition of the VASPI is only for subjects with painful peripheral neuropathy at Screening
- SF-36v2 ([Appendix 9](#))
 - Note: Administer SF-36v2 before conducting any other assessments on the same calendar day it is administered
- KCCQ ([Appendix 10](#))
 - Note: Administer KCCQ after the SF-36v2, but before conducting any other assessments on the same calendar day it is administered
- 6MWT ([Section 6.6.2.3](#)); collect HR and BP pre- and post-6MWT administration
 - Notes: Two pretreatment 6MWTs are required before the first administration of study drug, with a minimum of 4 days in between the two tests. The first Screening 6MWT is required to be performed between Days -28 and -5, at least 4 days prior to the second Screening 6MWT, which should be performed within 2 days prior to Month 1-Day 1 (i.e., on Day -2 or Day -1). NT-proBNP should be drawn before conducting 6MWT if being performed on the same calendar day.
- Echocardiogram (perform locally)
 - Note: If an echocardiogram was conducted within 90 days prior to Screening Day -28, it does not need to be repeated during Screening and the previous result may be used for eligibility; however, to be eligible for the additional cardiac imaging analysis, the subject must have had a 4-chamber view, 2-dimensional echocardiogram with Doppler
- 12-lead ECG performed in triplicate (perform centrally)
- Laboratory Assessments (central laboratory, unless otherwise noted):
 - Hematology and chemistry (including amylase and creatine kinase) per [Appendix 11](#)
 - PT/INR and PTT
 - Additional coagulation samples per [Appendix 12](#)
 - Troponin T
 - NT-proBNP

- Note: NT-proBNP should be drawn before 6MWT if being performed on the same calendar day
- Serum pregnancy test for WOCBP within 28 days before Month 1-Day 1 study drug administration
 - Note: Women with tubal ligations are considered to be of childbearing potential but women who are surgically sterile (hysterectomy) or postmenopausal ≥ 2 years are not considered to be of childbearing potential
- Serum free light chains
- Serum immunofixation electrophoresis (IFE) and protein electrophoresis (PEP)
- Urinalysis - dipstick per [Appendix 11](#)
- Urinalysis - quantitative analysis/renal biomarkers per [Appendix 11](#)
 - Notes: It is important that the sample be taken before exercising and at approximately the same time for each collection; therefore, the first morning void is recommended. Urine samples will be collected and frozen for potential analysis at a later date.
- 24-hour urine collection for:
 - Urine IFE and PEP
 - Urine protein excretion
- Other Assessments (see Laboratory Manual)
 - Archive sample – collect only from those subjects who have consented to the collection and archiving of their samples for future correlative testing

6.1.2 Treatment Visits

Study visits will occur every 28 days based on scheduling from Month 1-Day 1. A ± 5 -day window is allowed for visits starting after Month 1. Subjects may receive up to 12 infusions of study drug; a minimum of 21 days between doses is required.

The predose assessments for each visit may be performed within the 3 days before the visit unless otherwise specified. Although central laboratory assessments will be performed each month for study analysis, local laboratory assessments may be performed for subject management when necessary for obtaining results on a more immediate basis. Results will be reviewed prior to dosing at each month's Day 1 visit to confirm that continued dosing is appropriate.

Subjects who present with symptomatic orthostatic hypotension and/or systolic BP <85 mmHg, which in the medical judgment of the Investigator would interfere with the subject's ability to safely receive treatment, will have study drug withheld until the next scheduled monthly administration, but should still have all other study visit assessments completed. If study drug is withheld and subsequently rescheduled, central laboratory assessments required for that visit will need to be repeated if they were drawn >7 days prior to the rescheduled dosing date. However, a symptom-directed physical exam and vital signs need to be repeated prior to each dosing.

6.1.2.1 Month 1-Day 1

Prior to Study Drug Infusion:

The following assessments will be done prior to dosing on Month 1-Day 1:

- Concomitant medications/therapies
- Assessment of AEs
- Directed physical examination - including weight and examination of the following: general appearance; head, ears, eyes, nose, and throat; neck; skin; cardiovascular system; respiratory system; gastrointestinal system; and nervous system. The components of the physical exam will be as clinically indicated; however, the following should be assessed: macroglossia, submandibular nodes/fullness, adenopathy, ecchymoses, liver/spleen size (palpable +/-), ascites (+/-), and edema (which should be quantified on a scale of 0-4).
- Vital signs including HR, BP, RR, and body temperature (per [Section 6.6.1.2](#)) – within 30 minutes before dosing, after subject has been at rest ≥ 5 minutes; assess in same position for all time points
- ECOG PS ([Appendix 7](#))
- NYHA class ([Appendix 8](#))
- NIS-LL ([Appendix 5](#)) and VASPI ([Appendix 6](#))
 - Note: NIS-LL is for all subjects with peripheral neuropathy at Screening and the addition of the VASPI is only for subjects with painful peripheral neuropathy at Screening
- 12-lead ECG in triplicate (perform centrally) within 30 minutes before study drug administration
- Laboratory Assessments (central laboratory, unless otherwise noted):
 - Hematology and chemistry (including amylase) per [Appendix 11](#)
 - Inflammatory biomarkers per [Appendix 11](#)
 - NT-proBNP

- Serum pregnancy test within 24 hours before study drug administration (local laboratory)
- Urinalysis - dipstick per [Appendix 11](#)
- Other Assessments (see Laboratory Manual)
 - NEOD001 serum sample – within 2 hours before infusion
 - Anti-NEOD001 serum sample
- Randomization – After the subject is randomized, study drug treatment may be initiated
- Ensure subject continues to meet eligibility criteria before administration of study drug

Study Drug Administration:

- Administer study drug IV over 120 (± 10) minutes ([Section 5.3](#))
- Vital signs including HR, BP, RR, and body temperature (per [Section 6.6.1.2](#)) – assess 60 (± 10) minutes after the start of the infusion; assess in same position for all time points

Assessments After Infusion:

- Monitor subjects for 90 (± 10) minutes following completion of the study drug infusion. The Investigator may increase this standard monitoring time if deemed appropriate or per local standards. In the event of any clinical concerns or suspicious signs or symptoms after the infusion, the subject will remain under observation for as long as the Investigator deems it appropriate.
- Vital signs including HR, BP, RR, and body temperature (per [Section 6.6.1.2](#)) after subject has been at rest ≥ 5 minutes; assess in same position for all time points:
 - At the end of infusion (EOI) (+5 minutes)
 - 30 (± 5) minutes after EOI
 - 60 (± 10) minutes after EOI
- 12-lead ECG in triplicate (perform centrally):
 - Within 15 minutes after EOI
- Other Assessments (see Laboratory Manual):
 - NEOD001 serum sample within 4 hours after EOI

- Collect additional blood samples if a significant toxicity is observed (e.g., a systemic infusion-related reaction, anaphylaxis, hypersensitivity reaction; [Section 5.4.2](#)) and if possible, samples should be collected while the acute symptoms persist
- Discharge subject from clinic if no immediate safety concerns and/or hypersensitivities are present after the postdose assessments and monitoring period. In the event of any clinical concerns or suspicious signs or symptoms after the infusion, the subject will remain with the Investigator and study staff for further observation until the Investigator deems the subject can safely leave the clinic.

